8.2. Statistical Analyses

8.2.1. Primary Analysis

The primary endpoint will be analyzed using a non-inferiority analysis. The difference in proportions between pregabalin and placebo in the per protocol population will be compared using a 2-sided 95% confidence interval (CI). Non-inferiority will be demonstrated if the upper CI bound is less than 0.10 (10%).

The primary analysis is based on the Per Protocol set and the primary endpoint proportion of patients with visual field deterioration. A 2-sided 95% confidence interval on the difference in proportions between pregabalin and placebo will be constructed using unconditional exact methods. To support interpretation of the primary analysis, an analysis as described above but based on the ITT population rather than the Per Protocol set, will be performed. In this analysis, patients with a decrease in ≥ 5 points at termination but no repeat visit will be treated as if they did have a repeat visit that confirmed the decrease.

8.2.2. Secondary Analyses

Mean Deviation

Change in mean deviation from baseline to termination will be computed for each subject. Baseline mean deviation will be the average of the two mean deviations from the Baseline visit, and termination will be the mean deviation at the Week 12 visit (or the last available after Day 1 for subjects who terminate early). If a repeat test was done at termination, the mean deviation from the repeat test will be used. For each subject, the worst eye (ie, the eye with the greatest decrease in mean deviation) will be used in the analysis. Change in mean deviation will be analyzed for the ITT population using analysis of covariance (ANCOVA), with treatment and center in the model and the baseline mean deviation as the covariate. Least squares means will be obtained from the model and a 2-sided 95% confidence interval will be constructed on the difference in least squares means between pregabalin and placebo.

Non-inferiority with respect to mean deviation will be demonstrated if the lower bound of the CI is greater than -2.0 dB.

Visual Acuity

Visual acuity (best-corrected, measured using ETDRS charts) is expressed in terms of number of letters correctly identified. Change in visual acuity from baseline to termination will be computed for each subject. Baseline will be defined as the last visual acuity assessment prior to receiving study medication, and termination will be the visual acuity assessment at the Week 12 visit (or the last available after Day 1 for subjects who terminate early). If acuity was assessed at a repeat visit at termination, the acuity from the repeat test will be used. For each subject, the worst eye (ie, the eye with the greatest decrease in visual acuity) will be used in the analysis. Change in visual acuity will be analyzed for the ITT population using ANCOVA, with treatment and center in the model and the baseline acuity as the covariate.

8.2.3. Other Safety Analyses

Other safety parameters, including adverse events, physical examination results, vital signs, body weight, clinical laboratory results, subject assessment of seizure frequency as compared to before taking study medication, and S-STS/C-SSRS will be summarized by treatment group, but not analyzed inferentially. Screening ophthalmologic assessment (Dilated Funduscopy), SBQ-R and self-administered Patient Health Questionnaire (PHQ-8) will be summarized for both treatments combined and by treatment group. Mental Health Risk Assessment (MHRA) will be summarized at screening, baseline and post treatment.

CCI
[Redacted text block]

8.2.3.2. Suicidal Ideation and Behavior Assessment (S-STC/C-SSRS)

Both S-STC and C-SSRS will be mapped to Columbia-Classification Algorithm of Suicide Assessment (C-CASA) codes described in [Appendix A.1.5](#) and will be summarized descriptively by visit using count (percentage) for each C-CASA category. Percentages in a given visit will be based on the number of subjects assessed in that visit in the respective treatment groups.

The S-STC and C-SSRS data will also be presented in data listing.

8.2.3.3. Ophthalmologic Assessment (Dilated Funduscopy), PHQ-8, SBQ-R, MHRA

The external eye exam and funduscopy examination (normal/abnormal/not done) conducted at screening will be summarized descriptively using count (percentage) by treatment group.

The 8-question PHQ will be summarized for each question by its response categories using count and percentages. Percentages will be based on the number of subjects who answered the question in the respective treatment groups.

Ophthalmologic assessment and PHQ-8 data will also be presented in data listing.

Summary, using count and percentages, and listing of screening Suicide Behavior Questionnaire (SBQ-R) will be provided by treatment group.

Mental Health Risk Assessment (MHRA) will be summarized at screening, baseline and post treatment and presented in a data listing

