6.2.4.2. The Following Additional Assessments will be Performed on Week 12 Only

- Physical exam;
- External eye exam;
- Collect blood samples for clinical laboratories.
 1. Blood chemistry.
 2. Hematology.

- Urinalysis;
- Urine pregnancy test (females of child-bearing-potential);
- Patient assessment of seizure frequency;
- Subjects will be recommended to withhold their morning dose of investigational product on testing days until ophthalmologic testing is completed.

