6.3. Follow-up Visit (Week 15 Visit)

Subjects will have the following assessments performed 15 weeks following randomization (or 2 weeks after final dose of investigational product).

- Review Dosing Diary and assess dosing compliance;
- Concomitant medication;
- Adverse events;
- Body weight;
- Complete C-SSRS Since Last Visit assessment;
- Review C-SSRS to determine if a MHRA is required.

Subjects who have had visual findings on Week 12 and subsequently confirmed will also have ophthalmologic tests done at this visit.

- Ophthalmic Examination.
 1. External eye examinations;
 2. Best corrected ETDRS visual acuity;
 3. Computerized automated perimetry (Humphrey 24-2 SITA standard) on both eyes with 5 minutes break between 2 eyes.

Visual findings that require follow-up beyond Week 15 will be supported by Pfizer.

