6.4. Subject Withdrawal

Subjects may withdraw from the trial at any time at their own request, or they may be withdrawn at any time at the discretion of the investigator or sponsor for safety, behavioral, or administrative reasons. If a subject does not return for a scheduled visit, every effort should be made to contact the subject. In any circumstance, every effort should be made to document subject outcome, if possible. The investigator should inquire about the reason for withdrawal, request the subject to return all unused investigational product(s), request the

subject to return for a final visit, if applicable, and follow-up with the subject regarding any unresolved adverse events.

If the subject withdraws from the trial and withdraws consent for disclosure of future information, no further evaluations should be performed and no additional data should be collected. The sponsor may retain and continue to use any data collected before such withdrawal of consent. If the subject withdraws early, all Week 12 activities are to be conducted:

- External eye exam;
- Best corrected ETDRS visual acuity;
- Computerized automated perimetry (Humphrey 24-2 SITA) on both eyes with 5 minutes break between 2 eyes;
- Body weight;
- Review Dosing Diary and assess dosing compliance;
- Concomitant medications;
- Adverse events;
- Physical exam;
- Vital signs (sitting blood pressure, heart rate);
- Collect blood samples for clinical laboratories.
 1. Blood chemistry;
 2. Hematology;
- Urinalysis;
- Urine pregnancy test (females of child-bearing-potential);
- Complete C-SSRS Since Last Visit assessment;
- Review C-SSRS to determine if a MHRA is required.

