7. ASSESSMENTS

7.1. Ophthalmic Examination Procedures

7.1.1. External Eye Examinations

An external eye examination will be performed to assess the general appearance of the eye. It will look at ocular motility to detect deviations from strabismus or a convergence defect.

The external eye examination will be conducted at the Screening (Visit 1) and Week 12 (Visit 6) visits, and at the Week 15 (Follow-up, Visit 7) visits if deemed necessary.

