6.3. Other Endpoints

Screening ophthalmologic assessment (Dilated Funduscopy), SBQ-R and self-administered Patient Health Questionnaire (PHQ-8) will be summarized for both treatments combined and by treatment group. For subjects who require Mental Health Risk Assessment (MHRA), it may be assessed at screening, baseline and post treatment, eg, for those subjects who require evaluation.

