8. STATISTICAL METHODOLOGY AND STATISTICAL ANALYSES

8.1. Statistical METHODS

The primary analysis will compare the difference in proportions for the primary endpoint (based on a 2x2 contingency table combined across centers) using a 2-sided 95% confidence interval. Because it is expected that the proportions will be small for each treatment group, unconditional exact methods (StatXact or Proc-StatXact)² will be used to compute the confidence interval. Or the following code may be used.

```

/***
*** Hypothetic Example of calculated Exact approximation 95% CI
*** where there are 4 cases of deterioration and all 4 belong to PGB
***/

%macro pairs(x1px2=,nper=);
%do x1=0 %to &x1px2;
  data a;
  x2=&x1px2 -&x1;
  r=0; d=1; w=&nper-&x1; output;
  r=1; d=1; w=&x1; output;
  r=0; d=2; w=&nper - x2; output;
  r=1; d=2; w=x2; output;
run;
proc freq data=a;
```

```
tables d*r / norow nocol nopct exact riskdiff(cl=newcombe);  
exact riskdiff(method=score);  
weight w;  
output out=diffs riskdiff;  
  
run;  
  
data diffs2; set diffs;  
  
keep x1 n1 x2 n2 _rdif2 _x1_rdif2 xu_rdif2;  
x1=&x1; n1=&nper; x2=(&x1px2 - &x1); n2=&nper;  
  
run;  
  
proc append base=pairvary data=diffs2; run;  
  
%end;  
  
%mend pairs;  
  
*****;  
  
%pairs(x1px2=4,nper=142); * where there are 4 cases of deterioration  
and all 4 belong to PGB  
  
run;
```

Continuous measures (MD, visual acuity) will be analyzed using an ANCOVA main effects model, with treatment and study center in the model and the respective baseline score as a covariate. Output from the ANCOVA models will include adjusted (least squares) means and standard errors for each treatment group, p-values for the pregabalin versus placebo comparison, and 95% confidence intervals on the difference in LS means between pregabalin and placebo.

The only time point analyzed is Week 12 (or last observation, for patients who terminate early). Ophthalmologic data collected at Week 6 and follow-up will be summarized descriptively but not analyzed inferentially, unless it is used as the termination time point in the primary analysis

Centers with fewer than 4 patients will be combined with other centers prior to breaking the blind. Centers with 4 or more patients may be combined with other centers as needed, or may be left as separate centers. The pooling will be done geographically if possible. These pooled centers will be used in place of center in the analyses that include center in the model.

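### The visible SAP tabulates the external eye examination by arm at Screening only, although the protocol repeats it at Week 12 or early termination (minor)

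*SAP*

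**What the plan says.** **When the examination is done.** Protocol 7.1.1 states: "The external eye examination will be conducted at the Screening (Visit 1) and Week 12 (Visit 6) visits". It adds Week 15 where that is thought necessary. Protocol 6.2.4.2 lists "External eye exam" among the extra Week 12 assessments. Protocol 6.4 states: "If the subject withdraws early, all Week 12 activities are to be conducted", and the external eye examination heads the list that follows. On Week 15, Protocol 6.3 states: "Subjects who have had visual findings on Week 12 and subsequently confirmed will also have ophthalmologic tests done at this visit". The activity schedules in the protocol and in SAP 2.1 agree with this.

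**What is tabulated.** SAP 8.2.3.3 states: "The external eye exam and funduscopy examination (normal/abnormal/not done) conducted at screening will be summarized descriptively using count (percentage) by treatment group". The same section adds: "Ophthalmologic assessment and PHQ-8 data will also be presented in data listing". SAP 6.3 states: "Screening ophthalmologic assessment (Dilated Funduscopy), SBQ-R and self-administered Patient Health Questionnaire (PHQ-8) will be summarized for both treatments combined and by treatment group", and SAP 8.2.3 repeats this in substance. SAP 8.1 states: "Ophthalmologic data collected at Week 6 and follow-up will be summarized descriptively but not analyzed inferentially", with an exception for data that serve as the termination time point of the primary analysis.

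**The concern.** Two examinations with different schedules share one sentence and one visit restriction. Funduscopy is a Screening procedure (Protocol 7.1.2), so a Screening-only table reports all of it. The external eye examination looks at the general appearance of the eye, ocular motility, strabismus and convergence, and it is repeated after dosing. The sentence keeps the pre-dose half and leaves out the half that could differ by treatment.

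The Screening table will also carry little information. Protocol 4.2 excludes subjects with clinically significant abnormal findings on ophthalmologic examination and names the external eye examination. Among randomised subjects the table should show almost no clinically significant abnormality, whatever the drug does.

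This is a post-authorization safety study about vision, done as a regulatory commitment. What is at stake is whether its report shows, side by side, how many subjects in each arm developed a new external eye abnormality.

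**Working it through.** No sample size, margin or rate enters, so there is nothing to recalculate. The check sets the visit schedule against each visible SAP provision that could produce a by-arm summary.

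| Visit | Who is examined | Relation to dosing | By-arm summary of the external eye examination in the visible SAP |
|---|---|---|---|
| Screening | All | Before dosing | Yes, SAP 8.2.3.3 |
| Week 12 or early termination | All | Week 12 is on treatment; early termination may follow the last dose | None found |
| Week 15 | Subjects with confirmed Week 12 visual findings | About two weeks after the last dose | Descriptive summary under SAP 8.1, arm not stated |

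Week 12 counts as on treatment because Protocol 5.4.2 dispenses the taper supply at that visit.

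The SAP provisions in turn:

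1. **SAP 8.2.3.3** names the examination and limits its table to Screening.
2. **SAP 6.3 and 8.2.3** refer to the Screening ophthalmologic assessment and identify it as dilated funduscopy. They do not reach Week 12.
3. **SAP 8.1** provides descriptive ophthalmologic summaries for Week 6, when this examination is not scheduled, and for follow-up. Its statement that Week 12 is the only time point analysed follows the methods for the primary endpoint, mean deviation and acuity, and adds no external eye table.
4. **SAP 8.2.5** has rows for visual field deterioration (Per Protocol and ITT), mean deviation and visual acuity only.
5. **Protocol 9.4.5, SAP 6.2 and SAP 8.2.3** list other safety parameters. Physical examination is named and the external eye examination is not.
6. **SAP 5.3** says in general terms that remaining safety data are summarised on the ITT population. It fixes the population, not which visits of this examination are tabulated.

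Taken literally, the plan summarises the examination before dosing and, for a selected subset, after the taper, but not at the visit in between. The SAP does state later timing where it wants it. In 8.2.3.3 the mental health risk assessment is summarised at screening, baseline and post treatment, and 8.2.3.2 summarises the suicidality scales by visit.

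Size: two examinations are scheduled for every subject and a third is conditional. With about 187 subjects enrolled, at most about 187 Week 12 or early-termination results lack a dedicated by-arm table.

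**The case against.** The case on the other side has real substance.

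- **Physical examination.** Protocol 7.3 schedules one at Week 12 that covers eye movements, pupils, nystagmus and confrontation fields, and its results are summarised by arm. A reader might infer that the external eye examination is the only scheduled post-dose eye assessment besides acuity and the field test. The documents do not support that. The overlap on motility is genuine, though strabismus and convergence are specified only in Protocol 7.1.1.
- **Adverse events.** Under Protocol 8.5 an abnormal finding becomes an adverse event if it is symptomatic, needs work-up or treatment, changes dosing or participation, or is judged to be one. Adverse events are summarised by arm. The exemption in Protocol 7.1.4 concerns confirmed field deterioration without a complaint, not external eye findings. Findings that matter clinically therefore have a route to a table; an abnormality that meets none of the criteria does not.
- **Listing and general wording.** The listing sentence in SAP 8.2.3.3 carries no Screening limit, so Week 12 results probably appear subject by subject. The lists of other safety parameters are open-ended. A reader might infer that the Week 12 result goes unreported, and that is too strong. Still, a listing is not a comparison between arms, and a specific sentence limited to Screening outweighs general wording.
- **Redaction.** A block after the opening text of SAP 8.2.3 and one appendix entry are blacked out. They probably concern other topics, since 8.2.3.3 deals with this examination by name, but that cannot be confirmed.
- **Importance.** The examination is neither a primary nor a secondary endpoint, and the stated objective is visual fields. That stands, and it sets the severity.

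**Conclusion.** The point holds as a minor gap. In the visible text, the only dedicated by-arm table for the external eye examination uses its Screening result, and the Week 12 or early-termination result is left to a listing. Partial by-arm coverage comes from the physical examination and adverse events. This is a stated rule that fits one of the two examinations it governs, not just a missing detail.

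The effect is confined to one descriptive safety table. No endpoint, population, margin, power figure or non-inferiority conclusion changes. A reader might infer that the trial loses a formal between-arm test or a bound on the rate of new abnormalities. The documents do not support that: other safety parameters are deliberately descriptive, and the table proposed here would be descriptive too.

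The conclusion assumes that the redacted parts do not already supply the table and that the Week 12 form records the same normal, abnormal or not-done result as the Screening form. The description on treatment applies strictly to the Week 12 visit only.

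**What to change.** In SAP 8.2.3.3, give the two examinations separate sentences. Keep funduscopy at Screening. Summarise the external eye examination descriptively by treatment group at Screening and at Week 12 or early termination, with the count and percentage newly abnormal in each arm. A Screening-to-termination shift table would do this, with not done kept as a category. The more detailed layout is optional; adding the later visit to the existing by-arm summary closes the main gap.

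The cost is one SAP sentence and one table. The examinations are already scheduled, so no new data and no change to trial procedures are needed. The edit is best made before the blind is broken.

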8.2.4. Prior and Concomitant Medications

Prior and concomitant medications will be summarized for each treatment group. All medications will also be presented in data listing.

8.2.5. Summary of Safety Analyses

Endpoint	Analysis Set	Statistical Method	Model/ Covariates/ Strata	Missing Data	Interpretation
Proportion of patients with a deterioration in visual field threshold	Per Protocol	Confidence interval on difference	Treatment	Not Applicable	Primary Analysis. Subjects with a decrease in ≥ 5 points at termination are required to have a repeat assessment to be part of the analysis.
Proportion of patients with a deterioration in visual field threshold	ITT	Confidence interval on difference	Treatment	Not Applicable	Check for robustness of primary analysis. In this analysis, patients with a decrease in ≥ 5 points at termination but no repeat assessment will be treated as if they did have a repeat visit that confirmed the decrease.
Mean Deviation (MD)	ITT	ANCOVA	Treatment, Center/ Baseline MD	LOCF	Secondary Analysis
Visual Acuity	ITT	ANCOVA	Treatment, Center/ Baseline Acuity	LOCF	Secondary Analysis

10. APPENDICES

Appendix 1. DATA DERIVATION DETAILS

10.1. A.1.1 Definition and Use of Visit Windows in Reporting

Analyses will be conducted using change from baseline to the week 12 visit (or the last visit after Day 1 for patients who discontinue prior to week 12). Week 15 follow up assessments and for early terminators, the assessments conducted approximately 2 weeks after discontinuation of treatment will be excluded from analysis consideration.

For VFT and MD, Baseline and all other visits including the repeat visits will be based on the visits defined by the central reader in conjunction with the dates when treatment was administered. Additional considerations for determination of Visual Field Deterioration are given in [Appendix A.1.2](#).

For visual acuity the following week assignments will be used for the planned visits:

Time (Windowed Week)	Range (Days*)	Target Day
Baseline	[-99 to 1]	1
Week 6	[2 to 62]	42
Week 12	[63 to 95]	84
Week 15 Follow-up	≥ 96	105
LOCF** Week 12	[2 to 95]	84

*For purposes of windowing, a derived Day will be defined as (Visit Date-First Dose Date) + 1, where Visit Date is a follow-up visit that is greater than the baseline visit. Brackets indicate bound value is included in the window. In the case of two competing visits that are equally distant to the target day, the first visit will be selected as the assigned Week.

**LOCF imputation will be used only if the subject has missing data for Day 84 (Week 12), otherwise the Day 84 and Last Visit will be the same. If LOCF imputation is employed, then the first derived Day in the window closest to the target day will be chosen as the LOCF Week 12 assignment.

If visual acuity was assessed at a repeat visit or if there are multiple assessments at Week 12 window, then the latest of the assessments which is within the Week 12 window will be considered as the visual acuity at termination.

10.2. A.1.2 Additional Considerations for Determination of Visual Field Deterioration
Visual Field Deterioration:

There are 52 test points for each eye. Below is an eye map for visual field test.

1	A	B	C	D	E	F	G	H	I	J
2				2D	2E	2F	2G			
3			3C	3D	3E	3F	3G	3H		
4		4B	4C	4D	4E	4F	4G	4H	4I	
5	5A	5B	5C	5D	5E	5F	5G	5H	5I	5J
6	6A	6B	6C	6D	6E	6F	6G	6H	6I	6J
7		7B	7C	7D	7E	7F	7G	7H	7I	
8			8C	8D	8E	8F	8G	8H		
9				9D	9E	9F	9G			

There are 56 points in the above eye map. While testing the left eye, the points 5A, 6A, 5C, and 6C are left blank, of these 5C & 6C represent the blind spots, and 5A & 6A represent the points near the left ear. Similarly while testing the right eye, the points 5H, 6H, 5J, and 6J are left blank, of these 5H & 6H represent the blind spots, and 5J & 6J represent the points near the right ear.

Let T_i (where $i=1, 2, 3, \dots, 52$) represent the 52 test points for each eye. Each of these test points (for each eye and for each visual field test performed) contains a 1 (if abnormal at $p<0.05$) or a 0 otherwise.

Baseline is determined from the 2 tests performed at the baseline visit. For each eye, the baseline value of a test point is 1 only if that point was 1 at both baseline tests. That is, for a specific test point in a specific eye:

Value at 1st Baseline Test	Value at 2nd Baseline Test	Value to be Used as Baseline in the Analysis
0	1	0
1	0	0
0	0	0
1	1	1

Termination visual field deterioration is determined as follows:

If 5 or more test points that were 0 at baseline are 1 at termination for:

- a. either eye, then the patient will come in for a repeat visit. If the repeat visit indicates a 1 for at least 5 of the *same* test points in the *same* eye, then the patient is considered to have visual field deterioration.

- b. both eyes, then the patient will come in for a repeat visit. If the repeat visit has *at least one* eye with a 1 for at least 5 of the *same* test points, then the patient is considered to have visual field deterioration.

Programmatically, this would be done as follows: If the following condition: [$T_i=0$ at baseline, $T_i=1$ at termination and $T_i=1$ at the repeat test] (where $i=1, \dots, 52$ and T represents the test points) is true for ≥ 5 test points (T_1, T_2, \dots, T_{52}) for either eye, then that patient is considered to have visual field deterioration.

The following table gives some examples for 5 patients. (Assume that the left eye for Patients 1 and 2 and the right eye for Patients 3 and 5 are not shown because of no test points=1 at either baseline or termination.):

Patient/eye	Test points=1 at baseline	Test points=1 at termination	Test points=1 at repeat visit	Met criteria for deterioration
1/R	2D, 2E, 2F	2D, 2E, 2F, 2G, 3C	Not applicable	No, Repeat test not required since <5 new points = 1 at termination.
2/R	2D	3D, 3E, 3F, 3G, 3H, 4B, 4C	2D, 4E, 4F, 4G, 4H, 4I	No. None of the same test points were =1 at both termination and repeat test.
3/L	3C, 3D, 3E	2D, 2E, 2F, 4D, 4E, 4F	2E, 2F, 4D, 4E, 4F	Yes. 2E, 2F, 4D, 4E, 4F are =1 at termination and repeat visit and were not =1 at baseline.
4/R	2D, 2E, 2F, 2G, 3C, 3D	2D, 3E, 3F, 3G, 3H, 4B, 4C	3E, 3F, 3G, 3H, 4C	Yes. 3E, 3F, 3G, 3H, 4C are =1 at termination and repeat visit and were not =1 at baseline.
4/L	2D, 2E, 2F, 2G, 3C, 3D	2D, 3E, 3F, 4F, 4G, 4H	4F, 4G, 4H, 4I, 5B, 5D	No. <5 points = 1 at both termination and repeat tests.
5/L	3C, 3D, 3E	3G, 3H, 4B, 4C, 4D	Not done	Yes for ITT sensitivity analysis as the patient had 5 points=1 at termination that were 0 at baseline; patient excluded from primary analysis (Per Protocol set.) as the patient lacks a repeat test.

In these examples, Patients 3 and 4 are considered to have visual field deterioration and Patients 1 and 2 are not. Note that for Patient 4 only one of the eyes met the criteria on the repeat visit, but that was sufficient.

Confirmation (or lack of confirmation) of deterioration will be done programmatically, as specified above.

